Observational and Non-Interventional Study (ONIS) New Data Collection Protocol

Document Number:	c43224154-01				
BI Study Number:	1245-0340				
BI Investigational Product(s):	Empagliflozin				
Title:	Post Marketing Surveillance on Long Term Use of JARDIANCE [®] Tablets in Patients with Chronic Kidney Disease in Japan.				
Brief lay title:	Post Marketing Surveillance of JARDIANCE in Chronic Kidney Disease				
Protocol version identifier:	Version 1.0				
Date of previous version of protocol:	Not applicable				
PASS:	Yes				
EU PAS register number:	TBD				
Active substance:	Empagliflozin				
Medicinal product:	JARDIANCE [®] Tablets				
Product reference:	Not applicable				
Procedure number:	Not applicable				
Marketing authorisation holder(s):					
Joint PASS:	No				
Research question and objectives:	Study objective is to investigate the safety and effectiveness of long- term daily use of JARDIANCE [®] Tablets in patients with chronic kidney disease under real-world use.				
Country(-ies) of study:	Japan				

ONIS New Data Collection Protocol

Page 2 of 34

Study number: 1245-0340

Document number: c43224154-01

Proprietary confidential information © 2024 Boehringer Ingelheim International GmbH or one or more of its affiliated companies

Author:				
Marketing authorisation holder(s):				
In case of PASS, add: MAH contact person:				
In case of PASS, add:				
In case of PASS, add:	e-signature is on BIRDS			
Date:	22 Apr 2024			
	Page 1 of 34			
Proprietary confidential information				

© 2024 Boehringer Ingelheim Group of companies. All rights reserved. This document may not - in full or in part - be passed on, reproduced, published or otherwise used without prior written permission

ONIS New Data Collection Protocol

Page 3 of 34

Study number: 1245-0340

Document number: c43224154-01

Proprietary confidential information © 2024 Boehringer Ingelheim International GmbH or one or more of its affiliated companies

2. LIST OF ABBREVIATIONS

	A lower Dress Description
ADR	Adverse Drug Reaction
AE	Adverse Event
AESI	Adverse Event of Special interest
ALP	Alkaline Phosphatase
ALT	Alanine Transaminase
AST	Aspartate Transaminase
BI	Boehringer Ingelheim
BMI	Body Mass Index
BNP	Brain Natriuretic Peptide
BUN	Blood Urea Nitrogen
CHF	Chronic Heart Failure
CI	Confidence Interval
CKD	Chronic Kidney Disease
CRE	Creatinine
CRF	Case Report Form
eCRF	Electronic Case Report Form
DMRP	Data Management and Review Plan
EDC	Electronic Data Capture
eGFR	Estimated Glomerular Filtration Rate
ENCePP	European Network of Centres for Pharmacoepidemiology and
	Pharmacovigilance
ESKD	End Stage Kidney Disease
EU-QPPV	European Union – Qualified Person for Pharmacovigilance
γ-GTP	Gamma-Glutamyl Transferase
GPSP	Good Post- marketing Study Practice
Hb	Haemoglobin
Hct	Haematocrit
HDL	High Density Lipoprotein
IgA	Immunoglobulin A
IRB	Institutional Review Board
J-PMD Act	Japanese pharmaceuticals and Medical Devices Act
J-RMP	Japan Risk Management Plan
LDL	Low Density Lipoprotein
MAH	Marketing Authorisation Holder
MedDRA	Medical Dictionary for Drug Regulatory Activities
MHLW	Ministry of health, Labour and Welfare
NGSP	National Glycohemoglobin Standardization Program
NISnd	Non-interventional Cohort Study with New Data Collection
NT-pro BNP	N-terminal pro-Brain Natriuretic Peptide
ONIS	Observational and Non-interventional Study
PMDA	Pharmaceuticals and Medical Devices Agency
PMS	Post Marketing Surveillance
1 1110	

Page 6 of 34

Study number: 1245-0340

Document number: c43224154-01

DDC	D 1 D1 1 C 11
RBC	Red Blood Cell
SAE	Serious Adverse Event
SEAP	Statistical and Epidemiological Analysis Plan
SGLT-2	Sodium-Glucose Co-transporter-2
SGOT	Serum Glutamic Oxaloacetic Transaminase
SGPT	Serum Glutamic Pyruvic Transaminase
SOP	Standard Operating Procedures
T1DM	Type 1 Diabetes
T2D	Type 2 Diabetes
T2DM	Type 2 Diabetes mellitus
T-BIL	Total Bilirubin
T-CHO	Total cholesterol
TG	Triglycerides
UA	Uric Acid
UACR	Urine Albumin-to-Creatinine Ratio
UPCR	Urine Protein-to-Creatinine Ratio
WBC	White Blood Cell Count

ONIS New Data Collection Protocol

Study number: 1245-0340

Page 7 of 34 Document number: c43224154-01

Proprietary confidential information © 2024 Boehringer Ingelheim International GmbH or one or more of its affiliated companies

4. ABSTRACT

Name of company:				
Boehringer Ingelheim				
Name of finished medicinal product: JARDIANCE [®] Tablets				
Name of active ingre Empagliflozin	edient:			
Protocol date:	Study number:	Version/Revision:	Version/Revision date:	
22 Apr 2024	1245-0340	Version 1.0	Not applicable	
Title of study:		Surveillance on Long Term Use ronic Kidney Disease (CKD) in		
Rationale and background:	In Japan, post-approval execution of Post Marketing Surveillance is requested by the Japanese Pharmaceuticals and Medical Devices Act (J- PMD Act) in order to accumulate safety and effectiveness data for re- examination. Re-examination period is defined by J-PMD Act. Four years after approval of additional indication, results of PMS need to be submitted as a part of re-examination dossier to the Japanese regulatory authority, the Ministry of Health, Labour and Welfare (MHLW). Collected data from PMS will be included in the Japanese periodic safety reports and submitted to MHLW on designated dates until the end of re- examination period.			
Research question and objectives:	Study objective is to investigate the safety and effectiveness of long-term daily use of JARDIANCE [®] Tablets in patients with CKD under real-world use.			
Study design:	Cohort study Non-interventional, single arm study based on newly collected data Patients will be observed for up to 52 weeks after the start of the treatment with JARDIANCE [®] Tablets or until discontinuation of administration.			
Population:	 Inclusion criteria Patients with CKD who are prescribed JARDIANCE[®] Tablets for CKD according to the current Japanese package insert and who provided written informed consent prior to enrolment in this study. Patients who have never been treated with JARDIANCE[®] Tablets (including treatment for T2DM and/or CHF) before enrolment. Exclusion criteria None 			

ONIS New Data Collection Protocol

Page 9 of 34

Study number: 1245-0340

Document number: c43224154-01

Variables:	These outcomes are reported over the observational period.					
	Outcomes:					
	Primary outcome:					
	- Incidence of adverse drug reactions (focus on the safety specification on Japan Risk Management Plan (J-RMP): The events relevant volume depletion)					
	 Secondary outcomes: Kidney disease progression (defined as incidence of end-stage kidney disease, a sustained decline in eGFR to <10 mL/min/1.73m renal death, or a sustained decline of ≥40% in eGFR from baseline Incidence of cardiovascular death Incidence of all cause death Incidence of hospitalization for heart failure Change from baseline in eGFR to the last observation on treatment 					
Data sources:	Patients' data will be collected by electronic Case Report Form on Electronic					
	Data Capture system					
Study size:	800 (safety set)					
Data analysis:	Descriptive statistics will be summarised for safety and effectiveness.					
Milestones:	Planned start of data collection: 1 SEP 2024					
	Planned end of data collection: 31 MAY 2027					
	Study Report planned to be archived in 30 APR 2028					

ONIS New Data Collection Protocol

Page 10 of 34

Study number: 1245-0340

Document number: c43224154-01

Proprietary confidential information © 2024 Boehringer Ingelheim International GmbH or one or more of its affiliated companies

5. AMENDMENTS AND UPDATES

Number	Date	Section of study protocol	Amendment or update	Reason	
None					

ONIS New Data Collection Protocol

Page 11 of 34

Study number: 1245-0340

Document number: c43224154-01

Proprietary confidential information © 2024 Boehringer Ingelheim International GmbH or one or more of its affiliated companies

6. MILESTONES

Milestone	Planned Date
Start of data collection	1 Sep 2024
End of data collection	31 May 2027
Registration in the EU PAS register	TBD
Final report of study results:	2Q 2028

7. RATIONALE AND BACKGROUND

Chronic kidney disease (CKD) is a general term for heterogeneous disorders affecting kidney structure and function. In high-income countries, the prevalence of CKD is about 10% and is likely to increase as average population age rises and diabetes mellitus becomes more prevalent.(R19-0901, R13-2805)

Selective inhibition of sodium-glucose co-transporter-2 (SGLT-2) with empagliflozin causes urinary glucose excretion and reduces blood glucose, weight, plasma circulating volume and blood pressure. This has been shown to translate safely into reduced clinical risk from cardiovascular disease (particularly heart failure and cardiovascular death) in people with type 2 diabetes (T2D) and established cardiovascular disease. SGLT-2 inhibition with empagliflozin also reduces albuminuria and slows the annual decline in estimated glomerular filtration rate in people with T2D who still have preserved kidney function. The kidney effects may result from increased sodium delivery to the kidney's macula densa, which in turn causes glomerular afferent arteriolar vasoconstriction and reduced intraglomerular pressure. Raised intraglomerular pressure is believed to be central to the "final common pathway" of disease progression in CKD. Since SGLT-2 inhibition with empagliflozin also causes glycosuria and acute haemodynamic changes in kidney function in people without diabetes, empagliflozin may also be nephroprotective in conditions without ambient hyperglycaemia, which collectively account for 50 to 70% of patients with CKD worldwide. Patients with established CKD are at substantial risk of progressing to end-stage kidney disease despite the use of medical therapies, including renin-angiotensin system inhibition, so identifying new treatments to delay progression is a priority. Moreover, patients with CKD are at high risk of cardiovascular death and heart failure, which may also be reduced by empagliflozin. The number of patients treated with empagliflozin in 1245-0137 trial was 3292, including 292 from Japan. Since the high incidence of the events relevant volume depletion have been observed in Japanese patients (5.1% in empagliflozin 10mg group, 1.7% in placebo group) and further study is needed for "patients with eGFR less than 20 mL/min/1.73 m² or greater than 90 mL/min/1.73 m², UACR less than 200 mg/g, polycystic," etc., PMDA requested to collect more safety information of those patients.

This Post Marketing Surveillance (PMS) with 800 patients has been planned to collect the safety data (especially the events relevant volume depletion) according to the Safety Specification on the J-RMP and PMDA's request.

ONIS New Data Collection Protocol

Study number: 1245-0340

Proprietary confidential information © 2024 Boehringer Ingelheim International GmbH or one or more of its affiliated companies

In Japan, post-approval execution of Post Marketing Surveillance (PMS) is requested by the Japanese Pharmaceuticals and Medical Devices Act (J-PMD Act) in order to accumulate safety and efficacy data for re-examination. Re-examination period is defined by J-PMD Act. Four years after approval of combination drugs, results of PMS need to be submitted as a part of re-examination dossier to the Japanese regulatory authority, the Ministry of Health, Labour and Welfare (MHLW).

Collected data from PMS will be included in the Japanese periodic safety reports and submitted to MHLW on designated dates until the end of re-examination period.

The protocol may be revised because of new information or knowledge obtained in the course of conducting PMS. When a change of the approved label such as in dosage and administration or indications is made during the re-examination period of JARDIANCE[®] Tablets (except that for this change a re-examination period is newly designated by MHLW) and finds it necessary to revise this protocol, handling each matter should be discussed and the protocol may be revised. If any issue or concern arises (e.g. suggestion of a potential for clinically significant adverse reaction, remarkable increase in incidence of an adverse reaction, or any issue or concern on safety or efficacy assessment made prior to the approval of JARDIANCE[®] Tablets) in the course of PMS, implementation of additional special surveillance or post-marketing clinical trial should be discussed to identify or confirm a cause or estimated cause of such issue. Special surveillance is defined by J-PMD Act. It means surveillance for long-term use or special patient population (elderly, renal/hepatic dysfunction etc.).

ONIS New Data Collection Protocol

Study number: 1245-0340

Document number: c43224154-01

Proprietary confidential information © 2024 Boehringer Ingelheim International GmbH or one or more of its affiliated companies

8. **RESEARCH QUESTION AND OBJECTIVES**

Study objective is to investigate the safety and effectiveness of long-term daily use of JARDIANCE[®] Tablets in patients with chronic kidney disease in real-world clinical settings in Japan.

9. **RESEARCH METHODS**

9.1 STUDY DESIGN

Non-interventional cohort study with new data collection (NISnd) (Observational)

9.2 SETTING

9.2.1 Study sites

Sites (hospital and general clinics) at which JARDIANCE[®] Tablets are available for prescription will be selected in Japan.

Planned number of sites: Approximately 250 Sites

A Good Post-marketing Study Practice (GPSP) personnel explains the objective and design of this study to investigators at study site and establishes a written contract with the head of the study site (e.g., hospital director).

9.2.1.1 Managing Site and Physician/Investigator Selection, Contracting and Training See ANNEX 3.

9.2.2 Study population

As this is a real-world, observational, non-interventional study where no specific treatment is mandated or withheld from the patients. No limitations are set up on background factors and their concomitant drugs in use of actual medical practice.

Inclusion criteria

- Patients with CKD who are prescribed JARDIANCE[®] Tablets for CKD according to the current Japanese package insert and who provided written informed consent prior to enrolment in this study.
- Patients who have never been treated with Empagliflozin (including treatment for T2DM and CHF) before enrolment.

Exclusion criteria None

ONIS New Data Collection Protocol

Study number: 1245-0340

Proprietary confidential information © 2024 Boehringer Ingelheim International GmbH or one or more of its affiliated companies

Registration period From 01 September 2024 to 28 February 2026

The registration method will be a central registration system. Patients who begin treatment with JARDIANCE[®] Tablets after the conclusion of the contract will be registered by entering necessary information in the Electronic Data Capture (EDC) system within 14 days from the day of treatment initiation (inclusive).

Patient registration will be stopped when the overall target number of patients for the study is reached.

9.2.3 Study visits

The patients will be observed for up to 52 weeks after the start of the treatment with JARDIANCE[®] Tablets or discontinuation of administration.

9.2.4 Study discontinuation

Boehringer Ingelheim (BI) reserves the right to discontinue the study overall or at a particular study site at any time for the following reasons:

- 1. Failure to meet expected enrolment goals overall or at a particular study site
- 2. Emergence of any effectiveness / safety information that could significantly affect continuation of the study, or any other administrative reasons
- 3. Violation of GPSP, the study protocol, or the contract by a study site, investigator or research collaborator, disturbing the appropriate conduct of the study

The investigator / the study site / research collaborator will be reimbursed for reasonable expenses incurred in case of study / site termination (except in case of the third reason).

ONIS New Data Collection Protocol

Page 15 of 34

Study number: 1245-0340

Document number: c43224154-01

Proprietary confidential information © 2024 Boehringer Ingelheim International GmbH or one or more of its affiliated companies

9.2.5 Flow chart

Time point	Observation period				
Item	Baseline	Week 12	Week 26	Week 40	Week 52 or at discontinuation
Registration	X*				
Demographics	Х				
Medical history / Concomitant disease	Х				
Previous medications	Х]
Administration status of JARDIANCE [®] Tablets	X (Record throughout the observation period)			tion period)	
Concomitant medications		X (Record thr	oughout the c	bservation p	eriod)
Concomitant therapy		X (Record thr	oughout the c	bservation p	eriod)
Blood pressure, pulse rate and body weight	(X)	(X)	(X)	(X)	(X)
Laboratory tests	(X)	(X)	(X)	(X)	(X)
Adverse events	X (Examine throughout the observation period)				
Pregnancy status	Х	Х	Х	Х	X
e-signature, eCRF transmit**			Х		Х

(X) : If applicable

* : Patients administered JARDIANCE[®] Tablets should be registered within 14 days from the day of first administration.

** : When an adverse event occurs or upon discontinuation, data should be entered into the eCRF and transmitted using the EDC system.

9.3 VARIABLES

9.3.1 Exposures

Exposure to JARDIANCE[®] Tablets is estimated as time from the day JARDIANCE[®] Tablets is initiated until the day the drug is last administrated on a patient-level (or the final contact with the patient during the regular observation period).

9.3.2 Outcomes

These outcomes are reported over the observational period.

ONIS New Data Collection Protocol

Page 16 of 34 Document number: c43224154-01

Study number: 1245-0340

Proprietary confidential information © 2024 Boehringer Ingelheim International GmbH or one or more of its affiliated companies

9.3.2.1 Primary outcomes

The primary outcome of this study is the incidence of ADRs (focus on the events relevant volume depletion).

The ADR definition and reporting is described in section 11.

There is no primary outcome for effectiveness as the primary objective of a PMS is evaluating safety.

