9.5 STUDY SIZE

800 patients (safety analysisset) will be included in the study. 1000 patients will be enrolled to attrition.

The proportion of patients with relevant volume depletion events in the empagliflozin group in the Japanese population of EMPA-KIDNEY trial was 5.1% (15/292). Assuming that proportion is the true proportion of patients that will experience relevant volume depletion events in this PMS study, the precision of the estimate of the proportion of the events relevant volume depletion would be approximately 1.5%, as one-sided width of the 95% confidence interval, if 800 Japanese patients are available as safety analysis population. Possible risk factor associated with the events relevant volume depletion is the concomitant diuretics, and the observed proportion of it was 19.5% (57/292) in the Japanese population of EMPA-KIDNEY trial. Assuming the true proportion of "yes" risk factor in the study is 19.5%, the true proportion of the events relevant volume depletion in the patient population with "yes" risk factor is 5.1%, and the true odds ratio of 2.5 for "yes" risk factors to "no" risk factor, the power to detect differences of the proportion of the events relevant volume depletion between "yes" risk factor and "no" risk factor at a two-sided significance level of 5% is 82% (which is more than 80%), when 800 Japanese patients are included in the PMS study.

ONIS New Data Collection Protocol

Page 19 of 34

Study number: 1245-0340

Document number: c43224154-01

Proprietary confidential information © 2024 Boehringer Ingelheim International GmbH or one or more of its affiliated companies

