9.7.3 Safety analysis

The safety analysis will include all patients who registered in the study and receiving the JARDIANCE[®] Tablets treatment at least one time except those who are found to have no observation after enrolment, invalid registration, or invalid contract with the site (see section 9.7). In general, safety analyses will be descriptive, based on BI standards, and focus on AEs related to the JARDIANCE[®] Tablets treatment.

AEs will be coded using the current version of the Medical Dictionary for Drug Regulatory Activities (MedDRA) and will be based on the concept of treatment emergent AEs. To this end, all AEs occurring between the initiation of JARDIANCE[®] Tablets prescribed at baseline visit and 7 days (inclusive) after the last administration will be considered 'treatment emergent'. An AE is considered to be an ADR if either the physician/investigator who has reported the AE or the sponsor assesses its causal relationship as 'related'.

The frequency of ADRs will be tabulated by system organ class and preferred term according to the current MedDRA version. The frequency of SAEs will also be tabulated likewise. The incidence of ADRs stratified based on patient demographics will also be displayed.

No imputation is planned for missing AE data except for missing onset dates which will be handled according to BI standard.

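### Section 9.5 sizes the study on volume-depletion events with no causality condition, but the primary outcome and main analysis count only events judged related

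*Protocol*

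**What the plan says.** **Outcome.** Protocol section 9.3.2.1: "The primary outcome of this study is the incidence of ADRs (focus on the events relevant volume depletion"). Section 9.7.1 builds the main analysis on the same outcome (number, percentage and confidence interval) and refers to section 9.7.3 for details.

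**What counts as an ADR.** Under section 9.7.3 an AE qualifies if the reporting physician "or the sponsor assesses its causal relationship as 'related"; either judgement is enough. The same section says safety analyses will "focus on AEs related to the JARDIANCE[®] Tablets treatment".

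**Named displays in section 9.7.3.** There are three:
- "The frequency of ADRs will be tabulated by system organ class and preferred term";
- "The incidence of ADRs stratified based on patient demographics will also be displayed";
- "The frequency of SAEs will also be tabulated likewise", the only one not limited by causality.

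**What the size rests on.** Section 9.5 starts from "The proportion of patients with relevant volume depletion events in the empagliflozin group" among Japanese patients of the earlier trial, 5.1% (15/292), and takes it as the true proportion for this study. Section 7 gives the same rate as "5.1% in empagliflozin 10mg group, 1.7% in placebo group", again simply as events.

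**What is collected.** Section 11.2 requires all AEs to be collected and reported, whatever their cause.

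**The concern.** The study was requested because volume-depletion events were more frequent on drug than on placebo in Japanese patients. Section 9.5 sizes on such events, but the main analysis keeps only those that pass a causality judgement. Unless every event is judged related, the ADR proportion is lower than the proportion used for sizing. The stated precision and power then describe a quantity that no named analysis reports.

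The filter may also not be neutral. Section 9.5 names concomitant diuretics as the risk factor of interest, and section 11.2 lists co-medication among the alternative explanations that bear on causality. Whether an event is counted can therefore depend on the exposure being studied, in a single-arm study with no comparator to reveal it.

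**Working it through.** **Inputs.** From section 9.5: N = 800; p = 0.051; diuretic prevalence 19.5%, so 156 users and 644 non-users; odds ratio 2.5; two-sided 5%. Assumed, because the documents give no figure: related share f = 100, 80, 60 or 40%.

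**Step 1, the plan's precision.** Half-width = 1.96 × √(p(1−p)/N) = 1.96 × √(0.051 × 0.949/800) = 0.0152. The stated 1.5 points reproduces.

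**Step 2, the plan's power.** Pooled two-proportion z-test: power = Φ[(|p₁−p₂| − 1.96·s₀)/s₁]. Here s₀ is the standard error of the difference under the pooled rate and s₁ the one under the separate rates.
- As written (5.1% in diuretic users): odds 0.051/0.949 divided by 2.5 give 2.10% in non-users; power 54%.
- With 5.1% in non-users: odds multiplied by 2.5 give 11.84% in users. Then s₀ = 0.02186, s₁ = 0.02728, and power = Φ[(0.0674 − 1.96 × 0.02186)/0.02728] = Φ(0.90) = 82%.

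Only the second reading reproduces 82%, so it is the baseline below. That the text places 5.1% in the other group is a separate matter. Both readings take an event rate, not an ADR rate, as input.

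**Step 3, apply the related share.** Replace 0.051 by 0.051 × f and hold the odds ratio at 2.5.

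| f | Rate | Expected patients with event (of 800) | Half-width (points) | Half-width ÷ rate | Power, rate in non-users | Power, rate in users (as written) |
|---|---|---|---|---|---|---|
| 100% | 5.1% | 41 | 1.52 | 30% | 82% | 54% |
| 80% | 4.1% | 33 | 1.37 | 34% | 75% | 47% |
| 60% | 3.1% | 24 | 1.19 | 39% | 65% | 40% |
| 40% | 2.0% | 16 | 0.98 | 48% | 53% | 31% |

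The absolute half-width narrows as the rate falls. Relative precision and power get worse.

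**Step 4, a filter that differs by diuretic use.** True rates are 11.84% in users and 5.1% in non-users.
- 60% related in users, 80% in non-users: 7.11% against 4.08%. The odds ratio is (0.0711/0.9289)/(0.0408/0.9592) = 1.8 and power is about 38%.
- 80% in users, 60% in non-users: 9.48% against 3.06%. The odds ratio is (0.0948/0.9052)/(0.0306/0.9694) = 3.3.

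The contrast can move either way. The documents do not settle which.

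**The case against.** **The full analysis plan is not shown.** Section 9.7 says it only summarises and leaves full detail to the SEAP. A reader might infer that a non-serious volume-depletion event judged unrelated will never be reported, or that every planned table is restricted to related events. The documents support neither. The SAE table has no causality limit, section 9.7.3 does not say its list is complete, and a general AE table may sit in the SEAP. This objection stands, and no general AE table is requested here. It does not remove the mismatch, because sections 9.3.2.1 and 9.5 fix different quantities within the protocol itself.

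**The all-cause status of 15/292 is inferred.** No section states it. The missing restriction and the placebo rate make it the likely reading, but not a certain one. This stands, and it is why section 9.5 should say which it is.

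**A downward bias is not established.** A reader might infer that the causality filter must understate the risk and the diuretic contrast. But either party's judgement suffices for an ADR, and section 11.2 counts known pharmacology and drug-class effects towards relatedness. Section 7 itself describes reduced circulating volume as an effect of the drug. ADR incidence is also a legitimate quantity in its own right, not a faulty measure of AE incidence. This stands.

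**Power matters less here.** Section 9.7 rules out formal hypothesis tests, and no comparison with 5.1% is planned. This stands in part: the consequence is limited, but section 9.5 still uses power above 80% to justify 800 patients.

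**Conclusion.** The point holds as a mismatch between the quantity sized and the quantity named for analysis. Section 9.5 uses a volume-depletion event proportion with no causality condition, while sections 9.3.2.1, 9.7.1 and 9.7.3 estimate the proportion with events judged related.

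The 1.5-point precision is not threatened. What weakens is relative precision (from 30% of the estimate to 34, 39 and 48%) and the power claim (from 82% to about 75, 65 and 53%) at related shares of 80, 60 and 40%. Even the 80% share falls below the 80% mark the protocol sets itself.

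These figures rest on three assumptions: that 15/292 is all-cause, the related shares chosen for illustration, and an odds ratio held at 2.5 with the base rate in non-users. The filter may depend on diuretic use, but its direction is not known. The choice of ADR incidence as primary outcome is not itself at fault.

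**What to change.** - Keep ADR incidence as the primary outcome.
- In sections 9.7.1 and 9.7.3, add the proportion of patients with any treatment-emergent volume-depletion AE regardless of causality, with its 95% CI, overall and by baseline diuretic use.
- In section 9.5, name that proportion as the quantity being sized, and state whether 15/292 is all-cause or drug-related.

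The cost is wording and one additional table. All AEs and concomitant medications are already collected, so no new data and no change in N are needed. The report will then show two volume-depletion proportions, which should be labelled clearly as all-cause and related.
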